5.4.3.2 Dose changes

Dose administrative records for all patients will be listed. For patients with dose change, reasons will be displayed.

5.4.4 Prior and concomitant therapy

No prior and concomitant therapy information is collected for this study.

5.5 Efficacy evaluation

Proportion of patients with clinical benefit as assessed by the investigator will be listed using FAS.

5.6 Safety evaluation

All safety analyses will be performed based on the safety set.

The overall observation period will be divided into two mutually exclusive segments:

- On-treatment period: from day of first dose of study medication to 30 days after last dose of study medication;
- Post-treatment period: starting at day 30+1 after last dose of study medication.

Adverse events (AEs)

Adverse events (AEs) will be summarized in tables to include only AEs that started or worsened during the on-treatment period, the treatment-emergent AEs. However, all safety data (including those from the post-treatment periods) will be listed and those collected during the post treatment period are to be flagged. The incidence of treatment emergent adverse events (new or worsening from baseline) will be summarized by system organ class and/or preferred term, severity (based on CTCAE grades), type of adverse event, relation to study treatment. Deaths reportable as SAEs and non-fatal serious adverse events will be listed by patient and tabulated by type of adverse event, throughout the study and for 30 days after the last dose of the study medication.

Other safety data

No laboratory tests, ECG, and vital signs will be collected.

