The main purpose of the amendment is to change the primary endpoint to safety to better characterize the long-term safety of the compound. In addition, the protocol has been amended to include the collection of all AEs (including non-serious AEs) and an investigator attestation of continued clinical benefit.

This roll-over study has been opened since 24-Jun-2013 with 9 total patients enrolled and 3 patients ongoing.

Changes to the protocol

Changes to specific sections of the protocol are shown in the track changes version of the protocol using strike through red font for deletions and red underlined for insertions.

The following changes have been implemented:

Section 1.2.1.2: Updated clinical experience section to include the results from a multicentre phase III study in patients with relapsed or relapsed and refractory multiple myeloma and included title for section 1.2.1.2.1 (Clinical pharmacokinetics and pharmacodynamics).

Section 2.1: The purpose of the study has been updated to better characterize the long-term safety of s.a. oral panobinostat in patients who are on s.a. oral panobinostat treatment in a Novartis-sponsored study and are benefitting from the treatment as judged by the investigator.

Section 2.2: The rationale for the study design has been updated to better characterize the long-term safety of s.a. oral panobinostat in patients being treated in a current Novartis-sponsored study and who are benefitting from treatment with s.a. oral panobinostat.

[figure not shown]
Section 2.4 and 2.5 added per new protocol template.

Section 2.6: Risks and Benefits section added per the new protocol template.

Table 3-1: Updated with revised study objectives. The primary objective is to evaluate long term safety data. The secondary objective is to evaluate clinical benefit as assessed by the investigator.

Section 4.1: Updated to clarify that all adverse events and serious adverse events will be collected continuously throughout the study and to specify that at every quarterly visit, the investigator is required to confirm that the patient continues to have clinical benefit and may continue receiving study treatment. Updated to include study termination by sponsor as another possible criterion for discontinuation.

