Section 5.3 Exclusion criterion #4 updated to clarify highly effective contraception methods and duration of contraception use after stopping study treatment (i.e. 6 months for male participants and 3 months for females). Exclusion criterion #5 added to exclude sexually active males unless they use a condom during intercourse while taking study drug and for 6 months after stopping treatment and should not father a child in this period. A condom is required to be used also by vasectomized men as well as during intercourse with a male partner in order to prevent delivery of the drug via semen

Previous Section 6.1.5 (Dose escalation guidelines) re-located to section 6.2 per the new template.

Previous Section 6.1.6 (Treatment duration) updated to Section 6.1.5 was modified to specify that at every quarterly visit, the investigator is required to confirm that the patient continues to have clinical benefit and may continue receiving study treatment.

Section 6.2 and 6.2.1 added per the new protocol template.

Section 6.3 added to include information for identifying potential drug-induced liver injury.

Previous Section 6.2 (Concomitant medications) updated to Section 6.4 and Section 6.4.1 added per the new protocol template.

Section 6.4 updated to clarify that no other investigational therapy should be given to patients and no anticancer agents other than the study medication (panobinostat) should be given to patients during the study. If such agents are required for a patient then the patient must first be withdrawn from the study.

Sections 6.6, 6.6.1 and 6.6.2 added/updated per the new protocol template.

Table 7-1: Updated to include investigator attestation of clinical benefit at every quarterly visit, collection of all adverse events, relevant medical history, monthly at home pregnancy testing for female patients of child bearing potential and the study evaluation completion eCRF page at the end of the 30 day safety follow up.

Section 7.1.3: Updated to specify that the investigator is required to confirm that the patient continues to have clinical benefit at every quarterly visit and may continue receiving study treatment.

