3.1 Description of study design

This is a multi-center, open-label study to better characterize the long term safety of s.a. oral panobinostat in patients being treated in a current Novartis-sponsored, Oncology OGD&GMA study and who are benefiting from the treatment with s.a. oral panobinostat as determined by the guidelines of the parent protocol (for which the study objectives have been met) and based on the investigator's clinical judgment.

This roll-over study will not include screening period as patients will transfer directly from the parent study and commence with panobinostat as soon as they are consented and meet inclusion criteria of the roll-over protocol. All patients must report to the study site for their first visit and commence study participation. At that time, a quarterly (12 +/- 2 weeks) supply of oral panobinostat will be dispensed to the patient or as per local practice.

Patients must return to the study center on a quarterly (every 12 +/- 2 weeks) basis for resupply of study medication at which time limited drug dispensing information will be collected. Changes in dosing which might occur any time during the study treatment will be documented on the dose administration page.

Patients may return to the study center more frequently at the physicians' discretion as clinically indicated or as per standard of care, however, data from these visits will not be captured in the eCRF, but rather only in the source documents at the study center.

Reported AEs/SAEs, defined as per standard Novartis guidelines, will be collected continuously throughout the study in the safety database.

Patients entering the roll-over protocol should be followed at the investigator's discretion for known and/or clinically notable AEs that occur on panobinostat treatment as described in the current version of the [Investigator Brochure].

[figure not shown]
Patients will continue to be treated in the roll-over protocol until they are no longer benefiting from the s.a. oral panobinostat treatment, develop unacceptable toxicities, withdraw consent,

are non-compliant to the protocol, the investigator feels it is no longer in the patient's best interest to continue s.a. oral panobinostat therapy, pregnancy occurs or the patient dies, whichever comes first.

A patient will reach the end of the study treatment when s.a. oral panobinostat treatment is permanently discontinued. A 30-day safety follow-up after last dose of study drug should be conducted.

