5.2 Data included in the analysis

Patients will continue to be treated in the roll-over protocol until they are no longer benefiting from the s.a. oral panobinostat treatment, develop unacceptable toxicities, withdraw consent, are non-compliant to the protocol, the investigator feels it is no longer in the patient's best interest to continue s.a. oral panobinostat therapy, pregnancy occurs or the patient dies, whichever comes first.

A patient will reach the end of the study treatment when s.a. oral panobinostat treatment is permanently discontinued. A 30-day safety follow-up after last dose of study drug should be conducted.

The study is expected to remain open for 5 years or until such time that enrolled patients no longer need treatment with panobinostat, whichever occurs earlier.

All data reported in the database will be included in the analyses.

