5.3 Analysis populations

The following populations will be considered in the data analysis:

Full Analysis Set (FAS): consists of all patients who received at least one dose of panobinostat after enrolling into the roll-over protocol.

Safety set: consists of all patients who received at least one dose of panobinostat after enrolling into the roll-over protocol.

FAS and safety set are defined the same.

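### Non-serious AE incidence is tabulated over everyone dosed, but Amendment 01 added non-serious AE collection with 9 enrolled and 3 ongoing; unless earlier events were recovered, it is biased downward

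*SAP*

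**What the plan says.** **Denominator and window.** SAP 5.6: "All safety analyses will be performed based on the safety set". SAP 5.3 defines that set: "Safety set: consists of all patients who received at least one dose of panobinostat after enrolling into the roll-over protocol". SAP 5.6 runs the on-treatment period from the first dosing day to 30 days after the last dose, and SAP 5.4.3.1 takes the first dose as the first intake in this study. SAP 5.2 adds: "All data reported in the database will be included in the analyses". Nothing separates patients or treatment time by protocol version.

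**What the amendment changed.** The Amendment 01 rationale says "the protocol has been amended to include the collection of all AEs (including non-serious AEs" and records the study's status as "with 9 total patients enrolled and 3 patients ongoing". The entry for Table 7-1 reads: "Updated to include investigator attestation of clinical benefit at every quarterly visit, collection of all adverse events". The entry for Section 7.1.7 brings AEs into the 30-day follow-up. The current protocol summary, under safety assessments, describes AE and SAE collection as running forward.

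**What points the other way.** The log entry for Section 4.1 reads: "Updated to clarify that all adverse events and serious adverse events will be collected continuously throughout the study". Protocol 4.1, 7.1.3 and 8.1.1 describe collection of all AEs during the study, with AEs counted from roll-over consent, and set no limit at the amendment date.

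**Data source.** SAP 3.1 says that AEs and SAEs "will be collected continuously throughout the study in the safety database", and SAP Table 2-1 names the same database for the primary objective. Protocol 7.1.3 sends all AEs and SAEs to the eCRF. The only AE route into the safety database that the protocol describes is for SAEs (Table 7-1 footnote and Section 8.2.2).

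**The concern.** An incidence table treats a dosed patient with no recorded event as a patient who had no event. That holds only if the event type was being collected while the patient was at risk. Amendment 01 indicates that non-serious AEs were added part-way through, after 6 of the 9 enrolled patients were no longer ongoing. If nothing was recovered, those 6 patients add to the denominator of every non-serious AE row and cannot add to the numerator. The 3 ongoing patients also carry pre-amendment time in which nothing was collected.

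The same amendment made safety the primary objective, with frequency and severity of AEs/SAEs as the endpoint. Protocol 10.4.1 sends the primary variable to Section 10.5.3, whose AE subsection plans these tables. SAP Table 2-1 describes the primary analysis as routine pharmacovigilance review, but SAP 5.6 plans the same tables. A shortfall in them would therefore make long-term tolerability look better than it was observed to be.

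**Working it through.** The plan gives no sample size, expected AE rate or precision target, so there is no figure of its own to reproduce. The check has two parts.

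**1. Does any passage provide for recovering earlier non-serious AEs?**

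- Protocol 4.1, 7.1.3 and 8.1.1 set scope (all AEs, from consent). They name no step for patients who had already left.
- Protocol 8.1.1 has one carry-in rule: parent-study AEs still ongoing at entry become medical history. It does not concern roll-over AEs from before the amendment.
- Protocol 9.2, 9.4 and 11.6 require source records, queries on missing values and explanation of missing CRF data. This is general data-quality text. It makes later entry possible but does not call for it.
- Protocol 10.4.3, on missing values for the primary objective, is marked not applicable.

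So recovery is possible but not provided for.

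**2. Size of the effect if nothing was recovered**

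Inputs from the Amendment 01 rationale: 9 enrolled and 3 ongoing, so 9 − 3 = 6 no longer ongoing.

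Assumptions that the documents do not settle: all 9 were dosed; none of the 6 was still in 30-day follow-up; event risk was equal across patients; *m* patients enrolled later.

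For a purely non-serious AE with true patient-level incidence *p*, the expected reported proportion is *p* × (3 + *m*)/(9 + *m*). The ratio to the full-collection rate is (3 + *m*)/(9 + *m*):

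| *m* | ratio |
|---|---|
| 0 | 3/9 = 0.33 |
| 3 | 6/12 = 0.50 |
| 9 | 12/18 = 0.67 |
| 20 | 23/29 = 0.79 |

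At *m* = 0, an event with *p* = 50% would be reported at 0.50 × 3/9 = 16.7%. An event in every patient could show at most 33.3%.

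Departures from the assumptions, at *m* = 0:

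- If half of the affected ongoing patients had the event only before collection began: 3 × 0.5/9 = 0.17.
- If 2 of the 6 were still in follow-up and are counted as fully observed: (3 + 2)/9 = 0.56.
- If half of the affected patients had the event as an SAE, which was collected: (3 + 6 × 0.5)/9 = 0.67 in the all-AE table.
- If everything was recovered: 9/9 = 1, and there is no bias.

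The value 3/9 is thus an illustration and not a bound. What is fixed is the direction: without recovery, the reported rate cannot exceed the full-collection rate.

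**The case against.** The strongest reply is that the premise cannot be confirmed. Neither the superseded protocol nor the CRFs are in the file. The evidence that non-serious AEs were not collected before is amendment-log text plus the forward-looking phrase in the summary, which does not say from when. The operative sections read as whole-study collection from consent, and the log itself calls the Section 4.1 change a clarification. Once all AEs became CRF data, the general data-completeness rules give a basis for entering earlier events. This stands to the extent that prospective-only collection is an inference. It does not remove the point. The log is used here only for what was added and how many patients were ongoing, and the SAP does not say whether the earlier period is covered.

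A second reply is that all safety data are listed, so readers can judge for themselves. Listings show recorded events; they do not show periods in which nothing was collected.

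A third is that a supplementary table may rest on 3 patients, selected because they were still on drug. That is true, and is why it should sit beside the Safety Set tables and not replace them.

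A reader might also infer that precision is overstated, because a term seen in nobody would be read as 0 of 9 when only 3 were observed. The documents do not support that as a fault in the plan: no confidence interval is planned for any AE rate, and a term with no events would not normally have a row. Nor do they show that SAE counts are short.

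**Conclusion.** The point holds in conditional form. The SAP applies one denominator and one risk window to an event type whose collection the amendment describes as added part-way through, and it does not say whether earlier events were entered. Unless they were recovered, non-serious AE incidence is biased downward. So are the all-AE, severity and relatedness tables, to the extent that non-serious events make them up.

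The size is uncertain. It is one third of the full-collection rate under the stated assumptions with no later enrolment, nearer to 1 with later enrolment or partial coverage, lower if the ongoing patients' events fell before collection began, and exactly 1 with full recovery. A reader might infer that the earlier events are known to be lost; the documents do not establish that. SAE and death tables are not shown to be affected, and no planned interval is wrong. This should be fixed because the tables carry the primary endpoint and the remedy is small. Confidence is medium, since the key premise is inferred.

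**What to change.** In SAP 5.6:

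1. State the date on which all-AE collection began, by site if it differs, and the number of patients covered from that date.
2. Keep all tables on the full Safety Set. Footnote the all-AE, severity and relatedness tables to say that non-serious AEs before that date were not systematically collected.
3. Add one supplementary table of treatment-emergent non-serious AEs. Its denominator is patients on treatment or in 30-day follow-up on or after that date. It counts AEs that started or worsened on or after it, and any recorded AE that began earlier is listed separately.
4. Reconcile the AE data source: SAP Table 2-1 and 3.1 name the safety database, while Protocol 7.1.3 uses the eCRF.

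If earlier non-serious AEs were entered retrospectively for all dosed patients, say so in SAP 5.6 and omit the footnote and the extra table.

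The cost is a short SAP addition, one footnote and one table. The start date must be obtained, because the amendment needed IRB/IEC approval before implementation and no passage gives the date. The extra table may have as few as 3 patients. It describes those still on drug or in follow-up at that date plus later enrolees, so it supplements the Safety Set tables.

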5.7 Other analysis

5.7.1.1 Interim analysis

There will be no interim analysis for this study.

5.8 CSR Section 9.7.2 – Sample size and power considerations

There will be no sample size calculation for this study. All consented patients who meet all the inclusion criteria and none of the exclusion criteria are eligible to receive panobinostat.

Clinical Development

LBH589 (Panobinostat)

CLBH589B2402B

Appendix 16.1.9: Documentation of statistical methods

Document type: Clinical Study Report - Appendix 16.1.9

Property of Novartis
Confidential
May not be used, divulged, published or otherwise disclosed without the consent of Novartis

Table of contents

	Table	of content	its	11
1		Introduct	tion	12
2	Defin	itions and	general methodology	12
	2.1 Study drug		12	
		2.1.1	Date of first administration of study drug	12
		2.1.2	Date of last administration of study drug	12
	2.2	Study da	ay	12
	2.3	Baseline		12
	2.4	Partial da	lates and imputation rules	13
	2.5	Screenin	ng failure	13
	2.6	Protocol	l deviations	13
	2.7	Patient d	demographics	13
	2.8	Patient d	disposition	14
	2.9	Study dr	rug exposure	14
		2.9.1		

1 Introduction

The statistical methodology used (Section 9.7) will be described and discussed in the main part of the clinical study report. In Appendix 16.1.9, details of the statistical methods and their justification are provided for the statistical reviewers.

The statistical analysis of this study will be performed by Novartis personnel. SAS® version 9.3 (SAS Institute Inc., Cary, NC, USA) will be used for all analyses. All data are part of the Clinical Database and will be exported to SAS® files for analysis.

2 Definitions and general methodology

2.1 Study drug

Study drug and investigational treatment refer to s.a. oral panobinostat (hereof defined as the study treatment).

2.1.1 Date of first administration of study drug

The date of first administration of study drug is derived as the first date when a nonzero do se of study drug was administered and recorded on the dose administration record (DAR) eCRF. For the sake of simplicity, the date of first administration of study drug will also be referred as the *start of study drug*.

2.1.2 Date of last administration of study drug

The date of last administration of study drug is defined as the last date when a nonzero dose of study drug was administered and recorded on the end-of-treatment eCRF.

2.2 Study day

Study days will be calculated relative to the first day of panobinostat which is Day 1. If the event date is greater than or equal to the first dose date, then study day will be calculated as:

Study Day = Event date - Date of first dose + 1.

Time from events prior of panobinostat to the start of panobinostat, e.g., time since diagnosis, study days will be calculated as:

Study Day = Event date - Date of first dose.

Note that, the day of first dose is day 1 and the day before the date of first dose is day -1, not day 0. If duration is calculated in months, the duration in days will be divided by 1 month = 30.4375 days.

2.3 Baseline

There will be no baseline defined for this study.

2.4 Partial dates and imputation rules

Partial dates will be listed as partial dates. For computing time/duration, imputation rules will be used to impute the partial dates. All events with a start date on or before the cut-off date and with an end date after the cut-off date will be reported as 'continuing at the cut-off date'. The same rule will be applied to events starting on or before the cut-off date and not having a documented end date.

Sometimes it may be necessary to impute a date to be able to calculate a specific statistic. If the day and month is missing, it will be replaced by July 1; if only the day is missing, it will be replaced by the 15^{th} of that month. For dates prior to treatment start, the treatment start date -1 will be used if this imputation makes the date later than the treatment start (for panels without standard imputation rules).

2.5 Screening failure

This roll-over study will not include screening period as patients will transfer directly from the parent study and commence with panobinostat as soon as they are consented and meet inclusion criteria of the roll-over protocol. Hence, screen failure is not applicable for this study.

2.6 Protocol deviations

Protocol deviations as specified in the VAP module 3 will also be identified, summarized and listed. The table below shows the project specific assignment of protocol deviation severity codes to each set used in this trial and identifies the deviation codes corresponding to each severity.

Code	Action	Deviation code
5	Exclude from all safety analyses	n/a
8	Exclude from all analysis	E06
49	Report relevant protocol deviation – include in all analyses	E01, E02, E03, E04, E05, E07, E08, E09, E10, C01, C02, O01, O02, O03, S01, S02, S03, S04, W01, W02, W03, W04

	Severity codes		
Analysis set	5	8	49
Safety analysis set	No	No	Yes

Note: 'Yes' means include in population, 'No' means exclude from population

